1.2.2 Clinical Data

Summary of results from clinical studies:

Studies with metformin in cancer patients are abundant including all tumor sites. Our group has recently finished an investigator-run trial looking at evidence of OXPHOS metabolism pre- and post-metformin.

We have shown that head and neck squamous cell carcinomas (HNSCC) have high mitochondrial OXPHOS metabolism in highly proliferative cells¹⁷. Also, there is high MCT4 expression in HNSCC cancer associated fibroblasts (CAFs) and in carcinoma cells with low proliferation rates¹⁷. MCT4 expression is a marker of pseudohypoxia, oxidative stress and enhanced glycolytic metabolism. We have demonstrated that there is metabolic coupling between highly proliferative carcinoma cells with high OXPHOS metabolism and low proliferative carcinoma cells and fibroblasts¹⁷.

Bikas et al. retrospectively studied the radioprotective effects of Metformin on RAI treatment in differentiated thyroid cancer (DTC) patients by looking at complete blood count (CBC). The study used two arms. The Metformin group consisted of 40 diabetic patients with DTC taking Metformin while the control group consisted of 39 patients with DTC, combination of diabetic or not diabetic, not taking Metformin at the time of RAI treatment. Blood parameters included hemoglobin, red blood cell count, white blood cell count, absolute neutrophil count, absolute lymphocyte count, and platelet count. CBC was recorded at one month, six months, and twelve months. Patients treated with Metformin post-RAI treatment showed less of a decrease in white blood cell (WBC) count. The differences in WBC count between the two groups was highly statistically significant at all time points (P< 0.0001, P<0.0027, and P< 0.0001, respectively). The most prominent decrease in WBC was in absolute neutrophil count. WBC levels of patient in the Metformin group were also shown to recover to baseline levels more quickly (Bikas 2016).

Metformin not only likely has radioprotective effects but may also have anticancer effects as well which could impact effect of radioactive iodine treatment. Retrospective studies have shown that diabetics treated with metformin have a cancer risk reduction of approximately 40% compared to diabetics not treated with metformin^{18, 19}. Other studies have also shown a reduction in the frequency of cancer with metformin use²⁰. Evans et al²¹ reported that the risk of subsequent cancer diagnosis was reduced in patients with type II diabetes who received metformin (with an odds ratio of 0.85 for any

metformin exposure *versus* no metformin exposure). The protective effect increased with greater metformin exposure (measured as total dose prescribed or total duration of use).

There are currently multiple completed and on-going clinical trials evaluating the effect of metformin in combination with standard treatment of a variety of malignancies including breast, colorectal, pancreatic, lung, gynecologic, and prostate cancer^{22, 24, 25}. There is one phase II study accruing subjects using paclitaxel plus metformin up to 2500 mg a day or placebo in recurrent or metastatic head and neck cancer²⁶

Metformin reduces mitochondrial OXPHOS metabolism and hence we expect it to reduce mitochondrial metabolism in carcinoma cells. We want to investigate metformin's effects on epithelial-stroma metabolic coupling and its ability to revert the high OXPHOS metabolism in carcinoma cells and revert the stroma to a less tumor permissive state in various cancers.

Secondary end points will look at quality of life metrics including the Vanderbilt Head and Neck Cancer Symptom Survey, University of Washington Quality of Life Questionnaire, EORTCQLQ-H&N35, and the Xerostomia Questionnaire (XQ) all of which have been validated and used in multiple clinical studies to-date.

1.3 Study Therapy

Description of the experimental product:

Metformin (N, N-dimethylbiguanide) is a biguanide that is best known for its use as first line therapy for type II diabetes patients (1). Metformin specifically inhibits the complex I (NADH:ubiquinone oxidoreductase) of the mitochondrial electron transport chain decreasing cellular respiration and the rate of ATP formation (2) (3) (4). This triggers the activation of the energy sensor AMP-activated protein kinase (AMPK) that regulates cell metabolism and shifts it towards an energy-sparing state (5). This leads to reduced hepatic glucose production, decreases intestinal absorption of glucose, and improves insulin sensitivity thereby increasing peripheral glucose uptake and utilization without causing hypoglycemia. It is an FDA approved medication for the management of type 2 diabetes mellitus with extensive safety data. In general, clinically significant responses are not seen at doses <1500 mg daily; however, a lower recommended starting dose and gradual increased dosage is recommended to minimize gastrointestinal symptoms. Extensive preclinical data now also support the effectiveness of metformin as an antineoplastic and radioprotective agent (6).

1.4 Dose Rationale and Risk/Benefits

Summary of known and potential risks and benefits, if any, to subjects:

Metformin's most serious toxicity is lactic acidosis, occurring in three of 100,000 patient-years of use. Risk is significantly reduced when metformin use is avoided in those patients with hepatic, cardiac, or renal compromise. However, metformin's risk of lactic acidosis may be overstated since the recent evaluation of metformin associated lactic acidosis cases from 347 trials showed that the risk of lactic acidosis with metformin was not significantly increased compared with other antiglycemic agents²⁷. Minor gastrointestinal upset is the most common toxicity, leading to cessation of therapy in less than 5% of individuals. Metformin does not induce hypoglycemia. The possible societal benefits are large since this will allow us to learn about the pharmacodynamic effects of metformin in RAI, allowing for radioprotection against myelosuppression, xerostomia, and other sequelae of radioactive iodine treatment. More broadly, this will allow us to gain new information on metformin's effect on mitigation of side effects of radiation, tolerability, and safety profile in a population of subjects with various cancers.

Description and justification for the route of administration, dosing regimen, and treatment period:

Metformin will be administered orally since this is the route of administration currently approved by the FDA. Beginning one week prior to planned RAI therapy, the drug will be initiated at a dose of 500mg orally daily for 3 days and will then be increased to 500 mg twice daily, and, if tolerated, further increased to 1000mg twice daily after day 6. Subjects will maintain 1000 mg twice a day dosing until their scheduled radioactive iodine treatment. Following radioactive iodine treatment, subjects will resume oral intake of metformin for two weeks at 1000 mg twice a day dosing

There are currently multiple ongoing studies using doses from 500 mg twice daily up to 2500 mg per day in the treatment arms. There are also studies using the extended release form for a dose of 1500 mg daily. We have chosen our starting dose and escalation regimen to minimize side effects. The chosen standing dose is based on metformin's therapeutic range (minimal therapeutic dose in diabetic patients is 1500-2000 mg a day)^{28, 29}. The time of planned exposure to metformin will be 3 weeks. We will allow a window of an additional 2 weeks in the event that there are delays in the treatment scheduling but no patients will receive metformin for more than 35 days.

Rules for dose modification: Toxicity monitoring, dose modification and treatment of complications:

Particular attention will be paid in the first three days of treatment. Patients will take 500 mg/day for 3 days. From day 4, 500 mg twice daily and then in 3 days dose escalation to 1000 mg twice daily will be achieved. A phone call on the day of each dose escalation will be made in order to evaluate the tolerability of the drug and also weekly thereafter. Patients will be instructed to contact the clinical investigators should any side effects occur during the study¹⁹.

In the event that an iodinated IV contrast dye load for CT scanning is required at some point during the metformin treatment period, the drug will be stopped the day before IV dye administration, as is the standard practice among patients taking metformin. However, IV contrast dye generally precludes treatment with RAI as the iodinated contrast competes with RAI and thus limits its effect. Therefore, it is extremely unlikely that any patient will be receiving iodinated contrast at the time of the study. Furthermore, this measure is generally considered to be conservative as the risk of lactic acidosis in patients taking metformin has not been shown to be higher than that of the general population after IV contrast dye in recent literature. Nevertheless, this measure is in compliance with current American College of Radiology guidelines^{30, 31}. Metformin will be resumed the day after RAI treatment completion at the last dose the subject was receiving prior to being held and if escalation was planned as previously described.

Toxicity will be evaluated using the most recent version (version 4) of the NCI toxicity criteria, i.e. the NCI Common Terminology Criteria for Adverse Events (CTCAE) version 4.0. The CTCAE provides descriptive terminology and a grading scale for each adverse event listed. A copy of the CTCAE can be found at <http://ctep.cancer.gov>.

Grade 1 toxicity: Patient will be maintained on full dose.
Grade 2 toxicity: Dose will be reduced by 50% until grade 1 or lower. If symptoms are not resolved the treatment will be discontinued definitively.
Grade 3 toxicity (probably or definitely drug related): Treatment will be interrupted and reassessment of toxicity will be performed daily. If toxicity is reduced to grade 1 or lower dose will be reduced by 50%. If toxicity is not resolved after 3 days the treatment will be discontinued definitively.
Grade 4 toxicity (probably or definitely drug related): Treatment will be discontinued definitively.

In case of grade 1 or 2 diarrhea (the most frequent side effect), concomitant loperamide will be provided and with grade 2 diarrhea the dose will be reduced by 50% until grade 1 or lower.

Risk benefit analysis

The risks using metformin are small in this protocol with strict inclusion and exclusion criteria. It is unknown if metformin improves outcomes in cancer but this study is designed to evaluate whether the sequelae of treatment with RAI are mitigated by use of metformin. Hence, the potential direct benefits to subjects in this study include the possibility of decreased myelosuppression, xerostomia, and other sequelae of RAI. Further, the possible societal benefits are large since this will allow us to learn about the

pharmacodynamic effects of metformin in RAI treatment, tolerability and safety profile. Metformin is a widely used drug with an extensive safety record. In order to further minimize the risk of toxicity, strict exclusion criteria will be applied. This trial could also lead to a better understanding of the properties of the cancer microenvironment. The hypothetical risk of loss of confidentiality is minimized by the layers of security in place as detailed above.

Potential risks:

There is a potential risk of development of side effects related to metformin administration. Most commonly reported side effects in 1-5% of patients are diarrhea, nausea, vomiting, and abdominal pain. An extremely low risk of lactic acidosis is present (0.001%) which is minimized by excluding patients with renal dysfunction, hepatic dysfunction, cardiac impairment, pulmonary impairment, or excessive alcohol use. There is also a risk of loss of confidentiality which will be minimized as outlined in the Risk Management Procedures section.

Potential benefits:

Metformin may provide a radioprotective effect and mitigate known sequelae of RAI. Furthermore, metformin may alter tumor metabolism and improve outcomes in various cancers. This study is designed to evaluate whether the sequelae of RAI are mitigated by metformin and thus some patients may benefit from this study by taking metformin. With regards to cancer benefit, this study is not designed to evaluate efficacy in cancer treatment and it is unknown if metformin improves outcomes in cancer. The study may have societal benefits by allowing us to learn more about the properties of metformin which could help future cancer patients.

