5.5 Preparation and Administration of Study Drug/Therapy

Metformin tablets will be provided by the Department of Otorhinolaryngology and will be coordinated through the Thomas Jefferson University Hospital Investigational Drug Service (IDS) Pharmacy. Drug will be stored in locked cabinet until given to the participants. A three week supply of metformin and placebo will be provided to subjects and the drug will be self-administered by the participants.

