5.8 Packaging

Metformin will be provided by the Department of Otorhinolaryngology and will be coordinated through the Thomas Jefferson University Hospital Investigational Drug Service (IDS) Pharmacy. The study drug will be packaged in 1 bottle containing 500mg tablets for a maximum of 3 weeks. The bottle will be labeled "take one tablet daily for three days then one tablet twice daily for three days then two tablets twice daily until the day before the RAI treatment. Resume two tablets twice daily the day after RAI treatment until the end of the bottle".

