5.10.3 Dispensing of Study Drug The study drug will be dispensed to the participants in 1 bottle containing approximately 69 500mg tablets for a maximum of 3 weeks. The bottle will be labeled "The bottle will be labeled "take one tablet daily for three days then one tablet twice daily for three days then two tablets twice daily until the day before the RAI treatment. Resume two tablets twice daily the day after RAI treatment completion until the end of the bottle." The amount of pills dispensed to every participant will be logged in the accountability logs by the pharmacist. The participant will be instructed to bring the bottle and all the pills that were not taken the day of his surgery. Regular study drug reconciliation will be performed only at the end of the study.

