5.11 Placebo

Placebo will be given as 500mg capsules twice daily. Placebo will be in capsule form. It will be stored in a locked cabinet until given to the participants at room temperature in the Thomas Jefferson University Hospital Investigational Drug Service (IDS) Pharmacy.

The placebo will be packaged in bottles containing approximately forty-two (42) 500mg capsules. The bottle will be labeled "take one capsule twice daily until the day before the RAI treatment. The day after RIA treatment completion, resume one capsule twice daily until the end of bottle.".

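### One 21-day bottle cannot cover the two-week scheduling delay allowed in section 1.4, so postponing RAI after the first dose shortens the post-RAI course day for day

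*Combined protocol and SAP*

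**What the plan says.** Section 1.4 plans three weeks of drug and then adds "We will allow a window of an additional 2 weeks in the event that there are delays in the treatment scheduling", followed by the limit that "no patients will receive metformin for more than 35 days". The Study Summary and sections 1.4, 5.2 and 6.1 all describe drug continuing for two weeks after RAI.

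The supply sections allow for three weeks only. Section 5.5: "A three week supply of metformin and placebo will be provided to subjects". Section 5.10.3 dispenses "1 bottle containing approximately 69 500mg tablets for a maximum of 3 weeks". Section 5.11 packs "approximately forty-two (42) 500mg capsules" for placebo.

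Both labels carry the patient up to the day before RAI and then set the stop by the bottle, not by a date. For metformin, section 5.8 has "Resume two tablets twice daily the day after RAI treatment until the end of the bottle" and section 5.10.3 has "Resume two tablets twice daily the day after RAI treatment completion until the end of the bottle". For placebo, section 5.11 has "resume one capsule twice daily until the end of bottle".

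Section 6.1 sets the start date from the planned RAI date, one week ahead, and treats the end of the bottle as the same moment as two weeks after RAI. Section 5.6 judges compliance from what is left in the bottle at the first visit after dosing ends.

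**The concern.** The end of the bottle and two weeks after RAI coincide only if RAI takes place on the date used to set the first dose. Once dosing has started, each day of postponement uses a day's supply that was meant for after RAI. The protocol foresees this case and allows up to two weeks for it, but the supply and the label do not accommodate it.

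The post-RAI course is 14 of the 21 planned drug days, so what is at stake is delivery of most of the intervention. The record is also at stake: a patient who obeys the label empties the bottle whether RAI was on time or late, so the planned compliance measure reports full adherence in both cases.

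**Working it through.** **Inputs.** Metformin label (5.8, 5.10.3): 1 tablet a day for 3 days, 2 a day for 3 days, then 4 a day. Placebo label (5.11): 2 capsules a day. Bottles: about 69 tablets (5.10.3) and about 42 capsules (5.11). First dose 7 days before planned RAI (6.1). Extra window 14 days and ceiling 35 days (1.4).

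**Reproducing the plan's figures.** Metformin over 21 days: 3×1 + 3×2 + 15×4 = 69 tablets. Placebo: 21×2 = 42 capsules. Both match, so neither bottle holds spare supply. The ceiling also reproduces: 21 + 14 = 35 days.

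**No delay.** Seven pre-RAI days use 3 + 6 + 4 = 13 tablets or 14 capsules. That leaves 56 tablets (56/4 = 14 days) or 28 capsules (28/2 = 14 days).

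**RAI postponed d days after the first dose, label followed at full dose.**
- Metformin: 69 - (13 + 4d) = 56 - 4d tablets left; (56 - 4d)/4 = 14 - d days.
- Placebo: 42 - 2(7 + d) = 28 - 2d capsules left; (28 - 2d)/2 = 14 - d days.

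Section 6.1 can also be read as no dose on the day before RAI. There are then 6 + d pre-RAI days, and (60 - 4d)/4 = (30 - 2d)/2 = 15 - d days remain. The loss per day of delay is the same.

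| Delay d | Tablets left | Capsules left | Post-RAI days, either arm | If no dose the day before RAI |
|---|---|---|---|---|
| 0 | 56 | 28 | 14 | 15 |
| 3 | 44 | 22 | 11 | 12 |
| 7 | 28 | 14 | 7 | 8 |
| 10 | 16 | 8 | 4 | 5 |
| 14 | 0 | 0 | 0 | 1 |

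**What the bottle count shows at d = 7.** Metformin: 13 + 28 = 41 tablets before RAI and 28 after, so 69/69. Placebo: 14 + 14 = 28 capsules before and 14 after, so 42/42. Both read 100%, while the post-RAI share taken is 28/56 = 14/28 = 50%. At d = 14 the count is still 100%, with no post-RAI drug on the main reading.

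**Supply needed to keep 14 post-RAI days.** An extra 4d tablets or 2d capsules. At d = 14 that is 56 tablets (3 + 6 + 29×4 = 125 in all) or 28 capsules (35×2 = 70 in all).

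**Reduced dose.** A metformin patient held at 500 mg twice daily uses 3 + 2(4 + 14) = 39 tablets before RAI at d = 14 and has 30 left, or 15 days. The shortfall therefore concerns metformin patients at full dose and placebo patients on the labelled dose.

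**The case against.** No stated figure is wrong: 69, 42, three weeks and 35 days are each correct. The defect is that the supply does not match the allowance.

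The problem also needs particular conditions. RAI must move after the first dose. A change before it does no harm, because section 6.1 ties the start to the planned RAI date. A slip of 10 or 14 days is longer than the whole lead-in. Staff must neither pause dosing nor issue more drug. The pharmacy holds stock, and the weekly calls in sections 1.4 and 5.3 could uncover an empty bottle. The 35 days is a safety ceiling, not a promised duration. All of this is fair and limits how often the problem can occur. It does not remove it: section 1.4 expressly allows the delay, the label tells the patient to keep dosing, and neither a pause nor a resupply is written down. In the Schedule of Events the next study visit after dispensing is Visit 2, which falls after the post-RAI course.

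A reader might infer that a short course would be invisible. The documents do not support that. The start date is determined at Visit 1, and section 9.2 lists hospital records, dispensing records and phone logs as source documents. Start date, RAI date and an empty bottle together give 14 - d. What stands is that section 5.6 plans only the bottle check.

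A reader might also infer that patients on a lasting lower dose would overrun the two weeks, or even the 35-day ceiling, by finishing the bottle. That is not established. Section 6.1 itself equates the end of the bottle with two weeks after RAI, and section 5.6 collects the bottle at about that time. The dose-reduction rules in sections 1.4 and 5.3 differ, and the tablet count is approximate. A fixed stop date settles the case either way.

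**Conclusion.** The mismatch is real and should be corrected. Under the written supply and labels, a postponement of d days after the first dose leaves about 14 - d post-RAI days, so the stated two-week course is not delivered in a situation the protocol permits. The pill count reads 100% regardless.

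This rests on labelled dosing at full dose, dosing continued through the delay, one bottle per patient, and bottle contents close to the stated approximate numbers; a few extra pills would shift the result by about a day.

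It would be tempting to conclude that the treatment comparison is biased. The documents do not show that. The frequency of such delays is not given, the shortfall at labelled dose is the same in both arms, the model in section 7.2 has no end-of-drug time point, and the effect on the blood-count contrast is unknown. The point concerns delivery of treatment and its record.

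**What to change.** - **Stop rule (5.8, 5.10.3, 5.11, 6.1).** Replace finishing the bottle with stopping 14 days after RAI, never beyond 35 days of drug, and returning whatever is left.
- **Resupply (5.5, 5.8, 5.10.3, 5.11).** When RAI is postponed after the first dose, issue 4 tablets or 2 capsules per day of postponement: 28 or 14 for a 7-day delay, at most 56 or 28. Amend the three-week supply wording in 5.5 and the three-week maximum in 5.8 and 5.10.3 to match; otherwise they would contradict the resupply.
- **Record (5.6).** Enter first and last dosing dates before RAI and first and last dosing dates after RAI, and report post-RAI days taken next to the pill count.

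The cost is revised labels and protocol text, four dates on the case report form, and extra pills for postponed patients only. If all 16 patients in each arm were postponed by the full 14 days, the total would be 16×56 = 896 tablets and 16×28 = 448 capsules. No endpoint, sample size or analysis changes.

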Diagnosis and Main Inclusion Criteria	Subjects with a biopsy proven diagnosis of differentiated thyroid cancer, and who have a scheduled appointment for definitive resection of the tumor followed by treatment with radioactive iodine at TJUH are eligible to participate.
Study Therapy, Dose, Route, Regimen	Metformin is the therapeutic agent in the protocol. The initial starting dose will be 500 mg orally daily for 3 days which then will be increased to 500 mg twice daily and, if tolerated, further increased to 1000mg twice daily after day 6. Subjects will maintain 1000 mg twice a day dosing or highest tolerated dosing until two weeks post radiation. Subjects will be randomized to 1:1 to take metformin or placebo.
Duration of administration and follow-up	The initial starting dose will be 500 mg orally daily for 3 days which then will be increased to 500 mg twice daily and, if tolerated, further increased to 1000 mg twice daily after day 6. Subjects will maintain 1000 mg twice a day dosing until two weeks post radioactive iodine treatment. The participant's medical records will be reviewed every three months, surveys administered, and CBC repeated over the course of one year according to the schedule outlined below
Reference therapy	None

Statistical Methodology	
The primary objective of the study is to estimate the impact of metformin on complete blood count and serum exosome profile following radioactive iodine treatment. All patients from whom samples are obtained both pre- and post-treatment will be included in the primary analyses. Blood counts will be compared between the RAI/Metformin group (N=16) and the placebo control RAI group (N=16). The estimated mean difference and associated 95% confidence interval will be calculated.
 
Analysis of secondary outcomes will be primarily descriptive and related to taste disturbance, xerostomia, and xerophthalmia.

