Schema	
32 patients with thyroid cancer who undergo primary surgical resection and subsequently require RAI treatment.
 
Preoperative blood and saliva
 
Thyroidectomy
 
Recovery for approx 6-8 weeks
 
Postoperative Pretreatment Metformin Blood and Saliva
  <pre> graph TD A[Postoperative Pretreatment Metformin Blood and Saliva] --> B[Randomized Metformin treatment* (n=30) or placebo treatment (n=30) 1 wk] B --> C[Post-metformin or placebo Pre-RAI Tx blood and saliva] C --> D[RAI Tx] D --> E[Post RAI blood and saliva] E --> F[Metformin or placebo Treatment** 2 wks] F --> G[Post-RAI Tx blood sample q 3mo x 12 mos] </pre> 
*Metformin (500 mg/day for 3 days followed by 500 mg twice daily for 3 days followed by 1000 mg twice daily from day 6 until RAI tx)
 
**Metformin (1000 mg twice daily for two weeks following RAI tx)

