4.2 Exclusion Criteria

1. Subjects who are pregnant or may become pregnant during metformin administration in accordance with radioactive iodine treatment guidelines.
2. Subjects on metformin for any reason during the preceding 4 weeks.
3. Diabetic subjects are eligible if they are not taking metformin, insulin or sulfonylureas.
4. Subjects who have received iodinated contrast dye. Metformin treatment can be started the day after subjects complete iodinated contrast treatment. If a CT scan with contrast is scheduled after screening and consent, the metformin treatment should be stopped the day before iodinated contrast administration. Metformin can be resumed on the day after last iodinated contrast was administered to the subject.
5. Patients with history of hepatic dysfunction or hepatic disease and abnormal liver function tests (previously documented alanine aminotransferase greater than 40 IU/dL and/or plasma aspartate aminotransferase greater than 45 IU/d). Patients who have a history of hepatic dysfunction or hepatic disease but whose most recent liver function tests have been documented as normal will be eligible to participate.
6. Patients with plasma creatinine level greater than 1.3 mg/dL.
7. Patients with plasma alkaline phosphatase greater than 190 IU/dL.
8. Patients with plasma bicarbonate less than 22 mEq/L or history of lactic or any other metabolic acidosis.
9. Patients with history of congestive heart failure.
10. Patients with myocardial ischemia or peripheral muscle ischemia.
11. Patients with sepsis or severe infection.
12. Patients with history of lung disease currently requiring any pharmacologic or supplemental oxygen treatment.
13. Patients with a current history (in the past 30 days) of heavy drinking which is defined in accordance with CDC definition as more than 8 drinks per week for women and more than 15 drinks per week for men. A standard drink contains .6 ounces of pure alcohol. Generally, this amount of pure alcohol is found in 12-ounces of beer, 8-ounces of malt liquor, 5-ounces of wine, 1.5-ounces or a "shot" of 80-proof distilled spirits or liquor (e.g., gin, rum, vodka, or whiskey). While on study, patients should limit their alcohol consumption to no more than 8 drinks per week for women and no more than 15 drinks per week for men. Patients who feel they cannot comply with this recommendation are not eligible.

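### For metformin patients below 1000 mg twice daily before the RAI hold, the documents give conflicting restart doses

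*Combined protocol and SAP*

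**What the plan says.** The protocol states the post-RAI metformin dose in three forms.

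- **Last dose received.** The closing sentence of the iodinated-contrast paragraph in Section 1.4 restarts metformin the day after RAI is completed, "at the last dose the subject was receiving prior to being held and if escalation was planned as previously described".
- **Fixed dose.** The dosing-regimen text of Section 1.4 says that "subjects will resume oral intake of metformin for two weeks at 1000 mg twice a day dosing". The schema footnote in the Study Summary reads "Metformin (1000 mg twice daily for two weeks following RAI tx". Section 5.3 also carries 1000 mg twice daily through the two weeks after RAI. The label text is "Resume two tablets twice daily the day after RAI treatment until the end of the bottle" in Section 5.8 and "Resume two tablets twice daily the day after RAI treatment completion until the end of the bottle" in Section 5.10.3. Tablets are 500 mg, so the label dose is 2000 mg a day.
- **Highest tolerated dose.** The Study Therapy row of the Study Summary says "Subjects will maintain 1000 mg twice a day dosing or highest tolerated dosing until two weeks post radiation". The next row, on duration, omits the alternative.

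Patients below full dose are foreseen. The step to 1000 mg twice daily is conditional on tolerance (Study Summary, Sections 1.4 and 5.2, Appendix A footnote G). The toxicity rules in Sections 1.4 and 5.3 halve the dose for grade 2 toxicity and after improvement from grade 3. No section provides a different label for these patients.

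**The concern.** All metformin patients pause for RAI and restart from a bottle they keep at home. If a patient was on a lower dose because of toxicity, the printed instruction raises the dose at restart, while another sentence of the protocol keeps it where it was. Staff who notice the difference have no single rule to cite.

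Two study purposes are affected. Safety and tolerability is a secondary objective (Section 2.2), and in these patients the post-RAI dose would depend on which page was followed. Compliance is judged from the returned bottle (Section 5.6). Without a record of the intended restart dose, a correctly followed lower dose cannot be told apart from missed tablets.

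**Working it through.** **Inputs.** About 69 tablets of 500 mg (5.10.3); first dose one week before RAI (6.1); one tablet daily for three days, one twice daily for three days, then two twice daily until the day before RAI (labels); two weeks of dosing after RAI; no more than 35 days on metformin (1.4).

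**1. Reproduce the tablet count.** 3 × 1 + 3 × 2 + 1 × 4 + 14 × 4 = 3 + 6 + 4 + 56 = 69. This matches the stated figure, so the supply assumes four tablets a day on all 14 post-RAI days.

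**2. Label dose against last dose.** Ratio = 2000 mg a day ÷ last daily dose before the hold.

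| Last dose before the hold | mg a day | Ratio |
|---|---|---|
| 1000 mg twice daily | 2000 | 1 |
| 500 mg twice daily (not escalated, or halved from full dose) | 1000 | 2 |
| 500 mg daily (halved from 500 mg twice daily, or never raised) | 500 | 4 |

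**3. Last-dose rule combined with emptying the bottle.**

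- Kept at 500 mg twice daily on days 4 to 7: used 3 + 4 × 2 = 11; left 69 − 11 = 58; 58 ÷ 2 = 29 more days; total 7 + 29 = 36 dosing days, one over the limit.
- Full dose on day 7, then halved: used 13; left 56; 56 ÷ 2 = 28 more days; total 35, exactly at the limit.
- Still at 500 mg daily through day 7: used 7; left 62; 62 more days; total 69.

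Section 6.1 equates the end of the bottle with two weeks after RAI. That holds only at full dose.

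**4. Pill count.** If the first of these patients stops after 14 days at 500 mg twice daily, 58 − 28 = 30 tablets come back. If the patient follows the label for 14 days, 58 − 56 = 2 come back.

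**5. How many patients.** The documents give no rate of dose reduction or non-escalation. As an assumption, take the 1–5% that Section 1.4 gives for the common side effects. The expected number among 16 metformin patients is 16 × 0.01 = 0.16 to 16 × 0.05 = 0.8. The chance of at least one is 1 − 0.99^16 = 15% to 1 − 0.95^16 = 56%. At an assumed 10% it is 1 − 0.9^16 = 81%.

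**The case against.** The strongest reply is that the sentence quoted from Section 1.4 closes a paragraph on contrast and may concern only a contrast hold. Its wording names RAI completion, so the RAI reading is the natural one, but the placement leaves doubt. On the contrast reading it sets no post-RAI dose. A conflict would still remain between the fixed dose on one side and the Study Summary's tolerated-dose wording and the toxicity reductions on the other. A reader might also infer that restart dates after contrast conflict, because Section 4.2 item 4 says "Metformin can be resumed on the day after last iodinated contrast was administered to the subject". That inference needs the contrast reading, so it cannot be combined with the RAI reading used here. Section 1.4 also calls contrast during the study extremely unlikely.

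Other replies hold in part:

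- The escalation clause may reconcile the texts for a patient who tolerated the drug but had not finished escalating. It does not cover a patient held back or reduced for toxicity.
- In Section 5.2 and Appendix A footnote G, the full-dose wording follows directly on the tolerance condition and can be read as conditional. The labels cannot be read that way.
- The grade 2 reduction lasts only until grade 1 or lower, and Section 5.3 ends treatment if symptoms have not resolved within three days. Few patients would therefore still be at 500 mg daily at the hold, and the fourfold case is a corner case.
- A reader might infer that the restart is unsupervised. Weekly calls (1.4, 5.3), the instruction to report side effects (6.1) and a sample within three days after RAI (2.1) argue against that. However, no call is specified for the restart day.
- Nothing says that the label takes precedence over the toxicity rules. It contradicts them without displacing them.

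**Conclusion.** The conflict is real and confined to metformin patients whose last dose before the RAI hold was below 1000 mg twice daily. For them the label dose is 2 times the last dose in the firmer case and 4 times in the less likely one. At 500 mg twice daily from day 4, the last-dose rule, the instruction to empty the bottle and the 35-day limit cannot all be met.

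A reader might infer that the whole arm is affected, since all metformin patients restart and the post-RAI weeks carry 14 × 2000 = 28,000 of 34,500 mg planned (81%). The documents do not support this: patients on full dose get the same restart dose from every passage, so that share does not measure what is in dispute. The number affected is probably small, but it rests on an assumed rate.

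The analysis is as randomized (Section 7.3), so the primary blood-count contrast stays defined. This should be fixed because a patient-held instruction can contradict the trial's own toxicity reductions. It does not undermine the primary analysis. The result assumes the RAI reading of the Section 1.4 sentence and the standard one-week lead-in.

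**What to change.** - Reconcile the Study Summary (Study Therapy and duration rows, schema), both statements in Section 1.4, and Sections 5.3, 5.8 and 5.10.3 with the toxicity rules in Sections 1.4 and 5.3. One stated restart rule should cover fully escalated, non-escalated and dose-reduced patients. The sponsor and investigator must decide which rule applies.
- Make the label, the tablet supply and the instruction to finish the bottle consistent with that rule, the two-week period and the 35-day limit.
- State whether the last sentence of the contrast paragraph in Section 1.4 means the RAI hold or the contrast hold.
- Record the restart dose on the CRF, so that the tolerability results and pill counts can be interpreted.

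The cost is protocol and label wording, a check of the bottle count and one CRF field. The design, sample size and analysis model do not change.
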